7.2 PARTICIPANT DISCONTINUATION/WITHDRAWAL FROM THE STUDY

Participants are free to withdraw from participation in the study at any time upon request.

An investigator may discontinue or withdraw a participant from the study for the following reasons:

- Pregnancy
- Significant study intervention non-compliance
- If any clinical adverse event (AE), laboratory abnormality, or other medical condition or situation occurs such that continued participation in the study would not be in the best interest of the participant
- Disease progression which requires discontinuation of the study intervention
- If the participant meets an exclusion criterion (either newly developed or not previously recognized) that precludes further study participation

The reason for participant discontinuation or withdrawal from the study will be recorded on the CRF. Participants who sign the informed consent form (ICF) and are randomized but do not receive study intervention may be replaced. Participants who sign the ICF, are randomized, receive study intervention, and are withdrawn or discontinued from the study will not be replaced, and will be included in the final statistical analyses.

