Results: The only statistically significant difference between the groups at baseline (Table 1) was the ADAS-Cog score, which was lower (better) in the metformin group. Compliance with metformin was as follows: 7.5% stopped metformin but continued in the study following ITT, 15% remained on 500 mg a day (1 tablet), 35% remained on 1000 mg a day (2 tablets), 32.5% remained on 1500 mg a day (3 tablets), and 10% tolerated the maximum dose of 2,000 mg a day (4 tablets). There were no serious adverse events related to metformin and the 7.5% of persons who were not able to tolerate metformin reported gastrointestinal symptoms. Fasting insulin increased appreciably more in the placebo group compared with the metformin group as expected, and this difference was close to statistical significance (13.8 vs. 4.7 IU/mL; p = 0.09). High sensitivity C-reactive protein (hs-CRP), a measure of inflammation and vascular risk,¹²⁰ and a correlate of memory impairment in our center¹²¹ decreased in the metformin group and increased in the placebo group (-0.3 vs. 1.0 mg/dL; p = 0.07). Weight decreased more in the metformin group (-2.7 ± 6.4 Kg) compared with the placebo group (-1.6 ± 4.5 Kg) but this difference was not statistically significant (p = 0.63). Table 2 below shows the comparison in the primary clinical outcomes of the study, changes from baseline to month 12 in the ADAS-Cog score, and the total recall of the Selective Reminding Test (SRT).

Table 2. Comparison of changes from baseline to 12 months in the ADAS-cog and total recall of the SRT between metformin and placebo. Crude (unadjusted) analyses are from T-tests. Adjusted analyses are from Analyses of Covariance adjusted for was the baseline score of the ADAS-cog.

	Metformin	Placebo	p
ADAS-Cog			
Baseline	12.0 ± 4.0	14.6 ± 6.1	0.02
Last visit	12.1 ± 3.8	12.8 ± 6.2	0.52
Crude difference	0.0 ± 3.3	-1.98 ± 5.5	0.06
Adjusted difference	-0.5 ± 4.1	-1.4 ± 4.1	0.34
Total recall SRT			
Baseline	34.2 ± 7.9	36.1 ± 9.5	0.32
Last visit	43.6 ± 9.1	41.5 ± 8.4	0.31
Crude difference	9.4 ± 8.5	5.7 ± 8.7	0.05
Adjusted difference	9.5 ± 6.1	5.4 ± 6.1	0.05

and was close to statistical significance ($p=0.06$). There were no differences in delayed recall of the ADAS-cog (0.7 ± 1.8 for metformin vs. 0.0 ± 2.5 for placebo; $p = 0.35$).

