There were no differences between metformin and placebo in changes in digit span backwards, the neuropsychiatric inventory, the mini-mental status exam (MMSE), paragraph recall, or ADCS Clinical Global Impression of Change for Mild Cognitive Impairment (CGIC-MCI).¹²² One person in the placebo group and none in the metformin group converted to dementia. We conducted linear regression models examining the relation of the metformin dose with the primary outcomes, changes in total recall of the SRT and the total score of the ADAS-cog. The highest metformin dose (1000 mg twice a day) was associated with a statistically significant increase of 5.3 ± 10.0 more words in total recall of the SRT ($p=0.03$) compared to those in the placebo group and those who could not tolerate metformin. There was no association between the highest metformin dose and changes in the ADAS-Cog (0.7 ± 4.8 ; $p = 0.56$). Based on these findings, we are proposing to change the metformin formulation to the better tolerated extended-release form (Glucophage XR® [reduced mass]), and to exclude participants who cannot tolerate at least 1000 mg of metformin a day, an approach adopted by the clinical trials of diabetes using metformin.¹²³

Both the SRT and ADAS-Cog scores improved in the placebo and metformin groups (increases in SRT total recall, decreases in ADAS-COG scores). Crude analyses showed a greater improvement in the SRT in the metformin group, but the difference for the ADAS-Cog favored the placebo group. However, after adjustment for baseline ADAS-Cog the metformin group showed significantly greater improvement in SRT total recall compared to placebo (difference in changes in total recall of the SRT of metformin vs. placebo = 4.4 ± 8.5 words) and the difference for the ADAS-Cog was attenuated and not significant. The results were similar for delayed recall of the SRT, in which the gain in words was higher in the metformin group (2.3 ± 2.5) compared to the placebo group (1.3 ± 2.3)

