7 DISCONTINUATION OF STUDY INTERVENTION AND WITHDRAWAL OF PARTICIPANT

7.1 DISCONTINUATION OF STUDY INTERVENTION

Discontinuation of IP does not mean discontinuation from the study, and remaining study procedures should be completed as indicated by the study protocol. If a clinically significant finding is identified (including, but not limited to changes from baseline) after enrollment, the investigator or qualified designee will determine if any change in participant management is needed. Any new clinically relevant finding will be reported.

If participants develop diabetes by HbA1c criteria (6.5% or higher), they will be referred to their physicians to decide about treatment for diabetes. This may lead to discontinuation of IP upon consultation with the study's safety officer at the DCC. However, participants will be invited to remain in the study and will be analyzed following intent to treat.

If the medication is not discontinued due to an SAE and the investigator believes that the participant could be re-challenged with the discontinued medication per standard clinical practice, then this may be attempted after discussion with the DSMB and approval by the Medical Monitor.

If the medication was discontinued due to an SAE, then there should not be an attempt to restart the medication.

Any discontinuation of study drug will be recorded on the Dose Change Log eCRF.

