- During follow-up, if the participant develops dementia, indicated by a clinical dementia rating summary score of 1 as determined in the previous follow-up assessment. If the participant demonstrates capacity, he/she may consent; if the participant lacks capacity but wants to continue participation, a legally authorized representative will need to provide consent after the participant's assent. It is important to point out that this approach respects the participant's decision at baseline to participate in the study, when he/she had the capacity to consent.

Participants will be given three trials to respond to the UBACC. If after three trials they do not have a perfect score, they will be determined to lack capacity to consent. The determination of lacking capacity to consent will lead to exclusion at baseline, and to the need for a legally authorized representative to provide consent during follow-up. We expect that the contingencies described above will occur in less than 5% of the participants in the study, who will have mild cognitive impairment at baseline.

Medical history, medications

Detailed medical, surgical, and psychological history, and all medications utilized, including a judgment as to whether they affect cognition (positively or negatively) will be collected at baseline. Psychiatric history, current and past history of depression, current anxiety, alcohol and other substance use, head injury, hypertension, cardiac disease, thyroid disease, other major medical conditions, and surgery are evaluated at the baseline visit. A full medical history will be obtained only at the baseline visit. Any report of events, or side effects will prompt a full history and physical exam at follow-up visit. A COVID-19 questionnaire will be administered at every visit.

Physical Assessments (vital signs, anthropometric measures, brief neurologic exam)

A brief neurologic exam will be conducted at the in-person screening visit. Participants must also be assessed for signs of congestive heart failure, pulmonary, liver or renal disease as contraindications to

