
Cognitive diagnoses

Cognitive diagnosis will be examined for inclusion and exclusion purposes and will also be examined as an exploratory outcome. For cognitive diagnosis transitions (i.e., conversion from MCI to dementia), an adjudication panel at the CCMC will conduct a meeting to arrive at a consensus regarding diagnosis at the

end of the study. This panel will be comprised of investigators [name], [name], and [name]. During the meeting, information of all the cognitive, functional and other clinical information of the participants will be presented, blind to study allocation. Evidence of cognitive deficits (based on the neuropsychological scores), evidence of impairment in social or occupational function (as assessed by the functional measures), and evidence of cognitive and social-occupational function decline will be the criteria used for the diagnosis of dementia.

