8.3.8 EVENTS REQUIRING A CHANGE IN IP DOSING

At each study visit, the investigator will inquire about the occurrence of events that require a change in IP dosing, which may include, but are not limited to, hospitalizations, surgeries, and procedures that require holding metformin. Clinical events such as the development of anemia and/or B12 deficiency, and the development of contraindications to metformin, such as New York Heart Association Class III or IV congestive heart failure, and renal or hepatic insufficiency deemed to be of clinical significance are other examples of events that may require a change in IP dosing. Changes in IP dosing, and the associated reason, will be captured on relevant eCRF pages. Events above pre-specified thresholds as outlined in the Data Safety Monitoring Plan will trigger a review by the DSMB to investigate the presumed cause and impact of these events. Such events are initially reviewed by a Data Coordinating Center (DCC) staff member to determine if an event threshold has been reached, at which time the study investigators and the DSMB will be notified.

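### Section 7.2 permits study withdrawal for not taking IP, or for progression that stops IP, in tension with the continued follow-up assumed in 7.1, 6.1.2, 8.1 and the ITT analysis

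*Protocol*

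**What the plan says.** Section 7.2 lists grounds on which an investigator may take a participant out of the study, not merely off IP. Two concern us: "Significant study intervention non-compliance" and "Disease progression which requires discontinuation of the study intervention". The section adds that participants withdrawn after receiving IP are not replaced and stay in the final analysis. It describes no visits after withdrawal.

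Section 7.1 states the opposite default: "Discontinuation of IP does not mean discontinuation from the study, and remaining study procedures should be completed as indicated by the study protocol". It applies this to participants who develop diabetes, who are invited to stay even if IP is stopped. Section 6.1.2 keeps participants in the study on the maximum tolerated dose and analyses them by ITT.

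Section 8.1 plans for cognitive progression without withdrawal. When a participant develops dementia, capacity is checked, and "if the participant lacks capacity but wants to continue participation, a legally authorized representative will need to provide consent". Later in the same section: "For cognitive diagnosis transitions (i.e., conversion from MCI to dementia), an adjudication panel at the CCMC will conduct a meeting", to be held at the end of the study.

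Section 9.4.2 sets an ITT comparison of FC-SRT at 18 months. Missing outcomes are handled by censoring weights and outcome prediction models under missing at random, using earlier FC-SRT scores, study arm and baseline variables.

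**The concern.** Under ITT, the participants whose outcomes most need to be kept are those who stop or do not take the drug and those who decline. Section 7.2 gives a site textual support for ending follow-up in both groups, while 7.1, 6.1.2 and 8.1 support keeping them. No threshold is given for what makes non-compliance significant. In a multisite trial, two sites could therefore treat the same participant differently and both be following the protocol.

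What is at stake is the month-18 FC-SRT score. Under 9.4.2 and 9.4.10 the tests on that score, overall and by APOE-ε4 status, decide whether to proceed to phase III. A score that is never collected can be modelled but not recovered.

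**Working it through.** The point is textual, so the check is to follow a participant through the sections and then ask what size the documents support.

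**1. A participant who stops taking IP.**
- 7.1: stays in the study and completes remaining procedures.
- 6.1.2: stays in on the dose tolerated, down from the maximum.
- 7.2: may be withdrawn from the study if the non-compliance is judged significant.
- The pilot, described in 2.2.7, followed the 7.1 course: "7.5% stopped metformin but continued in the study following ITT".

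**2. A participant who progresses to dementia.**
- 8.1: capacity check, then continued participation, with a representative's consent if needed.
- 7.2: may be withdrawn from the study if the progression requires stopping IP. This makes an IP stop a route out of the study, which 7.1 says it is not.
- Does any section say that cognitive progression requires stopping IP? Section 8.3.8 gives examples of "events that require a change in IP dosing, which may include, but are not limited to, hospitalizations, surgeries, and procedures that require holding metformin". It goes on to anemia, B12 deficiency and new contraindications. Cognitive progression is not among them, although the list is open-ended. The condition in the bullet may therefore seldom be met.

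**3. What a withdrawn participant contributes.** Being kept in the final analysis does not supply a month-18 score. The participant enters as a censored case. What the dropout adjustment can use depends on what drove the withdrawal:
- *Decline visible in the last FC-SRT:* handled, because that score is in the model.
- *Decline reported between visits:* not captured. FC-SRT and CDR are taken at the same six-monthly visits, and the monthly contacts cover adverse events and compliance only.
- *Non-compliance:* not captured directly. Compliance is discussed monthly (6.4), but no compliance term is listed in 9.4.1 or 9.4.2. For someone withdrawn before month 6, only baseline variables and arm are available.

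The adjustment is therefore partial, and weakest for the non-compliance ground.

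**4. Size.** The only relevant planning figure is the allowance for loss in 9.2.2. Reading the error rates there as two-sided 0.10 and 80% power, a two-sample t-test at Cohen D 0.3 needs 138.06, so 139 per arm and 278 in total, as stated. At 10% loss per year over 1.5 years, 278 / 0.9^1.5 = 325.6, so 326, also as stated. The plan thus allows for 326 − 278 = 48 missing month-18 scores (48/326 = 14.7%). It does not divide these by reason, so withdrawals under 7.2 may already be inside the allowance, and no loss of power can be claimed.

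The pilot gives no usable rate either. The 7.5% (0.075 × 40 = 3 people) who stopped short-acting metformin had gastrointestinal intolerance, which MAP would handle under 6.1.2 and 7.1, and they stayed in follow-up. On progression, "One person in the placebo group and none in the metformin group converted to dementia", which is 1 of 80 over 12 months. Neither figure is a frequency of investigator withdrawal on these grounds, so a bias cannot be computed from them.

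**The case against.** The strongest reply is that the sections can be read together. Section 7.1 governs leaving IP and 7.2 governs leaving the study. The 7.2 list is permissive. Section 8.1 is the specific rule for dementia, and a general bullet whose condition nothing else in the protocol triggers does not displace it. Section 9.4.2 also pre-specifies an adjustment that uses earlier scores, and every trial with voluntary withdrawal leaves some outcomes missing in ways that no model captures.

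Much of this stands. It rules out calling the sections a flat contradiction, and it makes the progression bullet the lesser concern. It does not answer the non-compliance bullet: the ground is live, undefined and discretionary, and it is the one the dropout model is least able to adjust for. Unlike voluntary withdrawal, this loss is one that the protocol itself permits and could avoid.

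A reader might go further and infer that 7.2 will remove decliners and non-takers in numbers that materially distort the primary result. The documents do not support that. They give no frequency of use, and they provide for continued participation after dementia. The likely directions also differ: losing decliners would tend to shrink a true benefit, while losing metformin non-takers would tend to enlarge it if they benefit less. Nothing ensures that the two cancel, but neither is there a basis for a net figure.

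**Conclusion.** The tension is real and can be verified in the text. Section 7.2 allows follow-up to end on grounds where 7.1, 6.1.2, 8.1 and the ITT analysis assume that it continues. If the grounds are used, month-18 FC-SRT scores are lost for reasons linked to adherence or decline, and the planned adjustment covers this only in part.

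The size of any bias cannot be computed and is probably small. That judgement rests on the discretionary wording, on the absence of any section making cognitive progression a reason to stop IP, and on the earlier FC-SRT scores in the missing-data models. No effect on power or on the phase III decision is claimed. The case for changing the text is that the loss is avoidable and the correction is cheap, not that a large distortion has been shown.

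**What to change.** Reconcile the non-compliance and progression bullets of 7.2 with 7.1 and 8.1, so that not taking or stopping IP does not by itself end the scheduled month 6, 12 and 18 assessments for participants who still consent. Leave the rules for stopping IP as written, and likewise the other 7.2 grounds (pregnancy, the participant's best interest, exclusion criteria). A short memo should tell sites how the sections now fit together.

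The cost is protocol wording, the memo, and a few off-drug visits with assessments that are already on the schedule.

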7.3 LOST TO FOLLOW-UP

A participant will be considered lost to follow-up if he or she fails to return for two consecutive scheduled 6-month-visits and is unable to be contacted by the study site staff.

The following actions must be taken if a participant fails to return to the clinic for a required study visit:

- The site will attempt to contact the participant and reschedule the missed visit within 30 days and counsel the participant on the importance of maintaining the assigned visit schedule and ascertain if the participant wishes to and/or should continue in the study.
- Before a participant is deemed lost to follow-up, the investigator or designee will make every effort to regain contact with the participant (where possible, three telephone calls and, if necessary, a certified letter to the participant's last known mailing address or local equivalent methods). These contact attempts should be documented in the participant's medical record or study file.
- Should the participant continue to be unreachable, he or she will be considered to have withdrawn from the study with a primary reason of lost to follow-up.

The site will record the last date of contact (due to study completion, participant withdrawal from the study, or death) in the eCRF as the termination date.

8 STUDY ASSESSMENTS AND PROCEDURES

The table below summarizes the study procedures during the 18 months of the study. There are procedures (questionnaires) that can be done remotely or in person, listed under the "Remote Module", and there are procedures that can only be conducted in person, listed under the "in-person" module. The window to complete screening procedures is 28 days. The window for 6-month follow-up visits is \pm 30 days. The window for monthly contacts is \pm 7 days. If a visit or contact is missed due to force majeure (e.g., hospitalization), a participant may continue in the study with the visit after the one missed. All brain imaging procedures should be conducted prior to starting study drug. Participants who completed the 18 months visit before the implementation of protocol 1.9 will be informed of the change in study duration and that they have completed the study. Participants in this situation who are awaiting follow-up brain

imaging (originally after the 24-month visit) will be invited to undergo the brain imaging procedures as soon as protocol 1.9 is approved and implemented.

		Screening/ Baseline	Titration 1,2, 3	Month 1,2	Month 3	Month 4,5	Month 6	Month 7,8	Month 9	Month 10,11	Month 12	Month 13,14	Month 15	Month 16,17	Month 18
REMOTE MODULE															
1	Telephone Screen	X													
2	UBACC ^a	X													
3	Remote Consent	X													
4	Demographics ^f	X													
5	Medical history ^f	X													
6	Medications ^b	X					X			X				X	
7	MAC-Q	X					X			X				X	
8	COVID-19 questionnaire	X					X			X				X	
9	GDS	X					X			X				X	
10	CDR (Participant) ^c	X					X			X				X	
11	ADCS-ADL-PI (Participant)	X					X			X				X	
IN-PERSON MODULE															
12	In-Person Consent (if not done remotely)	X													
13	Vital Signs ^d	X					X			X				X	
14	Phlebotomy ^d	X					X			X				X	
15	Laboratory tests ^d	X					X			X				X	
16	ECG ^d	X													
17	MMSE	X					X			X				X	
18	Paragraph Recall	X					X			X				X	
19	Brief neurological exam	X					X			X				X	
20	DSST	X					X			X				X	
21	TMT A and B	X					X			X				X	
22	Eligibility and Randomization	X													
23	FC-SRT	X					X			X				X	
24	MRI	X												X	
25	Amyloid PET	X												X	
26	Tau PET	X												X	
27	Titration	X													
28	Monthly Telephone Call	X	X	X	X	X	X	X	X	X	X	X	X	X	X
29	Drug Dispense	X			X		X		X		X			X	
30	Dose Log	X	X	X	X	X	X	X	X	X	X	X	X	X	X
31	Adverse Events	X	X	X	X	X	X	X	X	X	X	X	X	X	X
32	Protocol Deviation	X	X	X	X	X	X	X	X	X	X	X	X	X	X
STUDY PARTNER															
33	Study Partner Consent ^e	X													
34	CDR (Partner) ^c	X						X			X			X	
35	ADCS-ADL-PI (Partner)	X						X			X			X	
36	MBI	X						X			X			X	
37	Final Status														X

Table 7. Study Assessments and Procedures

- a: The UBACC test should only be performed if clinically indicated or if study personnel feel the participant does not have capacity to consent at any of the study visits, Screening included. Please refer to Section 8.1 for more information.
- b: The study team should take particular care to note if any diabetes medication has been taken during the study duration.
- c: A CDR will be completed with each study participant and their respective study partner at all visits (Screening/Baseline, Month 6, Month 12, and Month 18). A total composite CDR score will be calculated using the sum of the CDR scores of both the participant and the partner. An ADAS-PAC certified team member should perform the CDR.
- d: Screening labs, vitals, and ECGs must be collected before randomization. Baseline labs, vitals, and ECGs do not need to be collected if performed within 14 days of the Baseline visit. All neuropsychological batteries, questionnaires, and the brief neurologic exam do not need to be performed again if collected during Screening. The screening tests will serve as the baseline collection.
- e: Study partners must provide verbal consent. The investigator or designee (consent designee) will read a consent script to the study partner and document that the study partner verbally consented to the MAP study.
- f: Study teams may stop screening assessments if the participant clearly does not meet eligibility.

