1 PROTOCOL SUMMARY

1.1 SYNOPSIS

Title:

Metformin in Alzheimer's dementia Prevention (MAP)

Study Description:

Up to Protocol version 1.8, MAP was a 24-month phase II/III 1:1 randomized clinical trial of extended-release metformin (Glucophage XR [reduced mass]) 2000 mg (in 500 mg tablets) vs. matching placebo among 370 persons with amnestic mild cognitive impairment without diabetes in the prevention of cognitive decline among persons at risk for Alzheimer's dementia. Participants were assessed every six months for a total of 5 visits (baseline and months 6, 12, 18, and 24). Up to 186 participants were planned to undergo brain magnetic resonance imaging (MRI) at baseline and after the 24 months visit. Up to 186 participants were also expected to undergo amyloid (18F-florbetaben) positron emission tomography (PET) and tau (18F-MK-6240) PET at baseline and after the 24 months visit, independently of the MRI. For protocol version 1.9, the follow-up duration was decreased to 18 months (4 visits), and the sample size was decreased to 326, based on a reconsideration of the pilot data and assumptions supporting the original design. Follow-up and PET will be completed after the 18-month visit.

Objectives:

Primary Objective: To test the efficacy of metformin in the prevention of cognitive decline associated with Alzheimer's dementia, we will compare changes over 18 months in verbal memory performance, measured with the Total Recall Score of the Free and Cued Selective Reminding Test (FC-SRT)

Secondary Objectives: 1) Examine changes in global cognitive performance measured with the Alzheimer's Disease Cooperative Study, Preclinical

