Alzheimer Cognitive Composite (ADCS-PACC); 2) Compare changes in neurodegeneration (cortical thickness) ascertained on MRI between metformin and placebo; 3) Compare changes in cerebrovascular disease (white matter hyperintensities) ascertained on MRI between metformin and placebo; 4) Compare changes in whole brain amyloid β (A β) standardized uptake value ratio (SUVR) and in incident amyloid positivity from baseline to 18 months between the metformin and placebo arms ; 5) Compare changes in tau SUVR in a composite brain region comprising medial and inferolateral temporal cortex from baseline to 18 months between the metformin and placebo arms; 6) Compare changes in plasma Alzheimer's disease (AD) biomarkers over 18-month follow-up between metformin and placebo; 7) To examine APOE- ϵ 4 genotype and COVID-19 history as a modifier of the efficacy of metformin.

Endpoints:

The primary endpoint is changes from baseline to 18 months in verbal memory performance, measured with the Total Recall Score of the FC-SRT, between the metformin and placebo arms, following an intent to treat (ITT) approach. **The secondary endpoints** are 1) changes in global cognitive performance, measured with the Alzheimer's Disease Cooperative Study Preclinical Alzheimer Cognitive Composite (ADCS-PACC); 2) changes in neurodegeneration, ascertained as cortical thickness in areas affected by AD on brain MRI; 3) changes in cerebrovascular disease, ascertained as white matter hyperintensities (WMH) volume on brain MRI; 4) Changes in whole brain amyloid β (A β) SUVR and in incident amyloid positivity; 5) Changes in tau SUVR in a composite brain region comprising medial and inferolateral temporal cortex; 6) Changes in plasma AD biomarkers. The FC-SRT and ADCS-PACC, and the plasma AD biomarkers will be measured 4 times in the study (baseline and months 6, 12, and 18). The brain imaging measures will be measured twice, at baseline and 18 months. We will also explore incident amyloid positivity at 18 months as determined by a cutoff of A β from PET equal to 24 centiloids.

[figure not shown]
Study Population:

[figure not shown]

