Participant Duration:	The length of follow-up is 18 months. This could be extended by four months to allow for completion of procedures between randomization and start of investigational product (IP) and after the last follow-up visit.

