9.4 STATISTICAL ANALYSES

9.4.1 GENERAL APPROACH

Exploratory data analysis will be performed on the entire study sample. All variables will be checked for outlying and unusual observations to detect general patterns, identify gaps and inconsistencies in the data. Visual inspection will be performed by means of box plots, scatterplots, quantile plots and others. Outliers will be checked for possible data entry errors. Reported descriptive statistics for continuous variables will include the number of participants with non-missing observations, median, mean, SD, interquartile range and range, while statistics for categorical variables will include the frequency and percentage of participants in each category.

Adjustment for covariates. In the primary analysis, all models described below will be adjusted for, ApoE- ϵ 4 (as a binary indicator), age (continuous), self-reported sex (male or female) (categorical), baseline total recall FC-SRT score (continuous), MMSE score (continuous), BMI (continuous) and HbA1c level. Additional adjustment for site, BMI, gender, race, educational attainment, COVID-19 history, and white matter hyperintensity will be done as sensitivity analyses. Statistical tests will be two-sided.

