9.4.3 ANALYSIS OF THE SECONDARY ENDPOINT(S)

Analytic plan for secondary aims. Our secondary aims compare changes in the ADCS-PACC between metformin and placebo on an ITT basis. The analytic approach will be the same as described for the Primary Aim. This will also apply to outcomes measured at all visits, including the plasma AD biomarkers. We will also compare changes from baseline to 18 months between metformin and placebo in brain cortical thickness, white matter hyperintensity volume, brain amyloid SUVR, and brain tau SUVR. Since these analyses will have only 2 time points, we will use analysis of covariance to compare the mean changes from baseline to 18 months, adjusting for study site and other prespecified covariates in the primary analysis.

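### The imaging ANCOVA in 9.4.3 omits each imaging measure's own baseline and takes no account of late follow-up scans; both gaps are small and can be closed by wording

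*Protocol*

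**What the plan says.** **Model.** For the four imaging measures, Protocol section 9.4.3 states that "we will use analysis of covariance to compare the mean changes from baseline to 18 months", adjusting for site and for the covariates prespecified in the primary analysis.

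**Covariates.** Section 9.4.1 opens its list with "In the primary analysis, all models described below will be adjusted for" and then names APOE-ε4, age, sex, baseline FC-SRT total recall, MMSE, BMI and HbA1c. White matter hyperintensity appears only among the extra adjustments kept for sensitivity analyses. Baseline cortical thickness, amyloid and tau appear in neither list. Scan interval is not mentioned.

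**Nominal scan times.** The synopsis (1.1) says: "The brain imaging measures will be measured twice, at baseline and 18 months". Sections 3 and 9.1 define the imaging endpoints over the same period.

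**Actual scan times for a transition group.** Before version 1.9 the plan was different: "Up to 186 participants were planned to undergo brain magnetic resonance imaging (MRI) at baseline and after the 24 months visit". Section 8 then provides: "Participants who completed the 18 months visit before the implementation of protocol 1.9 will be informed of the change in study duration". Those in this group who still await follow-up imaging "will be invited to undergo the brain imaging procedures as soon as protocol 1.9 is approved and implemented". Section 8 sets windows for visits and monthly contacts but none for the follow-up scan. The synopsis also allows participation to run up to four months longer so that procedures before drug start and after the last visit can be completed.

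**The concern.** There are two separate points.

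First, read literally, change in an imaging measure is adjusted for baseline memory score but not for where that measure itself started. The outcome's own baseline is usually the most useful single covariate in an analysis of change. Omitting it gives up precision in a subset of at most 186 participants (about 93 per arm) for which the protocol states no power.

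Second, the transition group is scanned some time after month 18, with no stated limit, and its data are pooled with on-time scans under an 18-month label. If the measures, or the treatment effect on them, progress with time, the pooled estimate describes an average interval somewhat longer than 18 months. How these scans are handled should be settled before unblinding.

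**Working it through.** The protocol gives no SD, effect size, power or number affected for imaging, so there is no stated figure to reproduce. Everything below rests on labelled assumptions.

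**1. Gain from the imaging baseline**

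Assume an equal SD (σ) at both scans and baseline-to-follow-up correlation rho.
- Variance of unadjusted change: 2σ²(1 - rho).
- Residual variance after adjusting for baseline: σ²(1 - rho²).
- Ratio: (1 + rho)/2, so the cut is (1 - rho)/2.

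| rho (assumed) | Ratio | Variance cut |
|---|---|---|
| 0.5 | 0.75 | 25% |
| 0.7 | 0.85 | 15% |
| 0.9 | 0.95 | 5% |
| 0.95 | 0.975 | 2.5% |
| 0.98 | 0.99 | 1% |

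The comparison is with change that has no covariates at all. The gain would be smaller so far as age and the other listed covariates already carry the same information.

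**2. Effect of late scans on the estimate**

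Assume that a share f is scanned m months late and that the effect accrues linearly. The mean interval is 18 + f·m months, and the effect multiplier is 1 + f·m/18.
- f = 0.10, m = 6: 18.6 months, multiplier 1 + 0.6/18 = 1.033.
- f = 0.30, m = 6: 19.8 months, multiplier 1 + 1.8/18 = 1.10.
- Wider range, f = 0.05 to 0.30 and m = 3 to 9: 18.15 to 20.7 months, multiplier 1.008 to 1.15.

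**3. Noise from late scans**

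Let k be the mean 18-month change divided by the SD of change. The added variance, as a share of the variance of change, is f(1 - f)(k·m/18)².
- f = 0.10, m = 6: 0.25% (k = 0.5) to 1.0% (k = 1).
- f = 0.30, m = 6: 0.58% (k = 0.5) to 2.33% (k = 1).
- Largest case tried, f = 0.30, m = 9, k = 1: 5.25%.

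**4. Simulation**

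Settings: 93 per arm, late scans 6 months late, k = 0.75, effects in SDs of change.
- With no true effect, the mean estimate stayed within ±0.003 of zero at every late share tried (0, 10%, 30%).
- A true 18-month effect of 0.40 was estimated at 0.41 to 0.42 with 10% late and about 0.44 with 30% late, in line with step 2.
- Adding the scan interval as a simple covariate left those estimates essentially unchanged (about 0.41 to 0.42 and 0.44) and changed the standard error by less than 1%.
- Adding the imaging baseline moved the standard error from about 0.148 to 0.136 at rho 0.7, and from about 0.146 to 0.143 at rho 0.9.

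**The case against.** The strongest reply is that this is detail for the SAP, which section 10.1.9 says will be developed and which is not shown here. Many statisticians would also read analysis of covariance as including the outcome's own baseline, and the primary list does carry the baseline of the primary outcome. That lowers the importance of the point but does not remove it. Section 9.4.3 is not silent: it names the model and fixes the covariate set by reference, and an SAP that followed it literally would inherit the gap.

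It can also be said that 18 months is a nominal label. Imaging is described as following the month-18 visit, extra months for procedures are openly allowed, and the wording of section 8 asks for late scans promptly. This stands as a reason to expect short delays, but it sets no limit.

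The documents do not support several stronger readings that a reader might infer:
- **Bias between arms or type I error inflation.** Late scanning follows from enrolment date relative to version 1.9. Section 6.3 randomises 1:1 in permuted blocks within site, under blinding, so late scans should be balanced.
- **Unadjusted change.** The model has covariates; what it lacks is any scaling for time.
- **A material precision loss from mixed intervals.** The added variance is at most about 5% in the range tried, and usually far less.
- **An effect on the phase III decision.** Sections 9.4.2 and 9.4.10 rest that decision on FC-SRT in the whole sample and the APOE-ε4 subgroups.

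**Conclusion.** The point holds as a minor improvement to the analysis of secondary endpoints.

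As written, the imaging model adjusts for baseline FC-SRT but not for the baseline of the measure analysed. The cost depends on a correlation that the protocol does not give: worth having (15% to 25% of variance) at rho 0.7 to 0.5, slight (1% to 5%) at rho 0.9 or above. Both ranges assume equal SDs at the two scans.

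The late scans blur the time frame of the estimate. With an assumed 10% to 30% of scans six months late and linear accrual, it would be about 3% to 10% larger than an 18-month effect. The number affected and the length of delay are not stated. The protocol also does not say whether anyone was already scanned on the old 24-month schedule; any such participant would add to the spread.

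**What to change.** In section 9.4.3, and in the SAP before unblinding:
1. Name the baseline value of each imaging measure as a covariate in that measure's model.
2. Keep the late scans and use actual scan dates, either by rescaling change to 18 months or through a model in which the treatment effect depends on time. An additive covariate for scan interval is not enough, because it leaves the estimated effect where it was.
3. Add one sensitivity analysis limited to scans within a stated window around month 18.

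No new visits or scans are needed, and baseline imaging values are collected under the protocol. The protocol does not list scan date as a data item, so confirm that it is captured with the images. The one analytic downside is that rescaling assumes roughly linear change over the interval; the sensitivity analysis shows whether that matters.
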